
Datasets required to identify vaccinated individuals
	
 • Data from the National Clinical Data Store (NCDS). Information recorded on the National Vaccine Management Tool (VMT) and GPIT system (Primary care practice medical record database) flows to the

² Stock SJ, McAllister D, Vasileiou E, *et al.* COVID-19 in Pregnancy in Scotland (COPS): protocol for an observational study using linked Scottish national data. *BMJ Open* 2020;**10**:e042813. doi: 10.1136/bmjopen-2020-042813. Available from: [COVID-19 in Pregnancy in Scotland \(COPS\): protocol for an observational study using linked Scottish national data | BMJ Open](#)

	NCDS, from where it is cleaned and then linked to the COPS data. Relevant data of interest: vaccination date, type, dose.
Datasets required to identify outcomes of interest	
 Data from a number of sources that hold pregnancy, maternal and neonatal outcome data will be brought into the COPS study dataset. Sources include: SMR01, SMR02, national linked anomaly database, SICSAG critical care admissions, NRS deaths.

3.5: Study Variables

3.5.1: Study Outcomes

Maternal, pregnancy and neonatal outcomes of interest are listed in Table 2. In our main analyses, we will assess the risk of each outcome in vaccinated women and their unvaccinated controls (i.e. classifying each woman as having the outcome or not), and will not attempt to capture any differences between the groups in the time to these events. As noted in Table 2, there are different periods of risk for each outcome (referred to as “outcome-specific follow-up period” throughout this protocol). For example, women will be considered at risk of any miscarriage from conception up to 23⁺⁶ weeks gestation, and at risk for stillbirth from 24⁺⁰ weeks gestation to the end of pregnancy. Women without an observed outcome who had not completed follow-up to the end of the follow-up period for a specific outcome in either the pre-pandemic (i.e. outcome-specific follow-up period not completed before 01 March 2020) or in the pandemic time period (i.e. outcome-specific follow-up period not completed before date of data extraction) will not be eligible for inclusion in the analysis for that outcome.

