Longer term child outcomes, including immune function and infection, and neurodevelopment, will be addressed in future work as required.

Other adverse outcomes that are not specific to pregnant women, will be investigated separately for the whole population as part of wider adverse events monitoring in Scotland. If these analyses suggest any signals in the pregnant population, those outcomes would be investigated in the pregnant population using the COPS data infrastructure, as required.

Table 2: Maternal, pregnancy and neonatal outcome measures for monitoring of safety of COVID-19 vaccination in pregnancy

Outcome measure	Definition	Primary or secondary outcome?	Clean window requirement to identify incident cases	Timing of vaccination to be included	Post vaccination risk period to be examined	Estimated background risk of outcome (%)
Maternal outcomes						
Hypertensive disorders of pregnancy	See ICD10 code list. Note that hypertensive disorders can only be diagnosed at >20 weeks.	Primary	No prior record in this pregnancy	Any	Up to E plus PP	10.0
Venous thromboembolism	See ICD10 code list	Primary	No prior record in this pregnancy	Any	Up to E plus PP	0.15
Pregnancy-related bleeding	See ICD10 code list	Primary	No prior record in this pregnancy	Any	Up to E plus PP	30.0 (for postpartum haemorrhage)
ICU admission or death (any cause)	ICU admission as identified on SICSAG record Death from any cause	Primary	None (but exploration to be undertaken of reasons for any pre-vaccination ICU admission where these are documented)	Any	Up to E plus PP	Unknown
Pregnancy outcomes						
Miscarriage	Miscarriage at <24 completed weeks gestation	Primary	None	Up to 23w+6d gestation	Up to 23+6 gestation	10.0 – 20.0

• First trimester miscarriage	Miscarriage at <14 completed weeks gestation	Secondary	None	Up to 13+6 gestation	Up to 13+6 gestation	Unknown
• Second trimester miscarriage	Miscarriage at 14-<24 completed weeks gestation	Secondary	None	Up to 23+6 gestation	14+0 to 23+6 gestation	Unknown
Ectopic pregnancy	Ectopic pregnancy ending at any gestation	Primary	None	Up to 2+6 gestation	Up to E	1.0
Stillbirth	Spontaneous fetal loss at ≥24 completed weeks gestation Any cause of fetal death Losses related to termination of pregnancy excluded	Primary	None	Any	24+0 to E	0.4
Baby outcomes (live births only unless otherwise stated)						

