Any congenital anomaly (relevant pregnancy outcome only)	Any major congenital anomaly as defined by EUROCAT (including live born babies diagnosed at <28 days of age and affected pregnancies resulting in spontaneous loss at ≥20 weeks or termination of pregnancy at any gestation)	Primary	None	Up to 9+6 gestation	At E plus NN	2.7
• Any non-genetic congenital anomaly (relevant pregnancy outcome only)	Any major congenital anomaly as defined by EUROCAT, excluding anomalies with known underlying genetic basis as per standard EUROCAT rules (including live born babies diagnosed at <28 days of age and affected pregnancies resulting in spontaneous loss at ≥20 weeks or termination of pregnancy at any gestation)	Secondary	None	Up to 9+6 gestation	At E plus NN	2.3
Microcephaly	Congenital microcephaly (i.e. present at birth) OFC on delivery record <2SD below	Primary	None	Any	At E	2.0

	mean for sex and gestation at delivery by WHO-UK90 growth reference Babies with anencephaly excluded					
• Severe microcephaly	Congenital microcephaly (i.e. present at birth) OFC on delivery record <3SD below mean for sex and gestation at delivery by WHO-UK90 growth reference Babies with anencephaly excluded	Secondary	None	Any	At E	0.4
Preterm birth	Delivery at <37 completed weeks gestation	Primary	None	Up to 36+6 gestation	Up to 36+6 gestation	7.0
• Very preterm birth	Delivery at <32 completed weeks gestation	Secondary	None	Up to 31+6 gestation	Up to 31+6 gestation	1.0
Spontaneous preterm birth	Delivery at <37 completed weeks gestation following P-PROM or spontaneous onset of labour	Primary	None	Up to 36+6 gestation	Up to 36+6 gestation	4.0
• Spontaneous very preterm birth	Delivery at <32 completed weeks gestation following P-PROM or spontaneous onset of labour	Secondary	None	Up to 31+6 gestation	Up to 31+6 gestation	0.6
Small for gestational age	Birthweight <10th centile by WHO-UK90 growth reference	Primary	None	Any	At E	10.0
• Very small for gestational age	Birthweight <3rd centile by WHO-UK90 growth reference	Secondary	None	Any	At E	3.0
Low Apgar score	5 min Apgar <7	Primary	None	Any	At E	1.5
• Very low APGAR score	5 min Apgar <4	Secondary	None	Any	At E	0.5
Neonatal death	Death from any cause	Primary	None	Any	E plus NN	0.2
Extended perinatal mortality (total births)	Stillbirth or neonatal death from any cause	Primary	None	Any	Up to E plus NN	0.6

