Notes: If timing of vaccination during pregnancy is specified as 'any', this means that women vaccinated at any point from six weeks preconception to date of end of pregnancy (E) will potentially be included in the analysis dependent on the woman being followed-up to the end of the outcome-specific follow-up period. For longer term risk periods: E is date of end of pregnancy; PP is mother's postpartum period, i.e. 6 weeks following delivery (E to E+41); NN is baby's neonatal period, i.e. 4 weeks following live birth (E to E+27). The pregnancy specific maternal outcomes listed above require follow-up to the end of the postpartum period (E+41) for mothers and the end of the postnatal period (E+27) for babies.

3.5.2: Exposure

The primary exposure to be investigated in the analyses is **any** receipt of COVID-19 vaccine from six weeks before conception to the end of an outcome-specific exposure period within pregnancy (Yes/No). The exposure periods for vaccination varies for each outcome (referred to as “outcome-specific exposure period” throughout this protocol), as outlined in Table 2. For ectopic pregnancy, for example, the exposed group will include women who were vaccinated between six weeks before conception up to 2⁺⁶ weeks gestation, while for stillbirth the vaccine exposure period is extended up to the end of the pregnancy.

Subgroup analyses will be conducted where sample size permits, further stratifying women who received their COVID-19 vaccine within the outcome-specific exposure period by: (1) the number of doses received; (2) by the class of vaccine(s) received and; (3) by the type of vaccine(s) received. For the latter two subgroup analyses, we will exclude women who received multiple different classes or types of vaccine within the outcome-specific exposure period. These results will need to be interpreted with caution given that some types of vaccination will be linked to specific sub-groups of women. For example, early in the vaccination programme women who were frontline health or care workers were more likely to receive the Pfizer/BioNTech vaccine, whereas women who were clinically (extremely) vulnerable were more likely to receive the AstraZeneca vaccine. There is therefore potential for residual confounding in comparative analyses examining outcomes following receipt of specific vaccine types.

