For the matched cohort study, the primary comparison for each outcome will be between women vaccinated in the six weeks preceding conception or up to the end of the outcome-specific exposure period within pregnancy and unvaccinated pregnant women from the pre-pandemic period. Only women who had been followed-up to the end of the outcome-specific follow-up period on the 29 February 2020 are eligible to be controls for that outcome analysis. Women who have COVID-19 infection from six weeks preconception up to the end of the outcome-specific follow-up period will

not be eligible for inclusion in the vaccinated group for this primary analysis. Each individual in the pregnant vaccinated cohort will be matched to three individual unvaccinated pregnant controls, if possible⁵. Different pregnancies from a single woman can be matched to different cases, and if a case had a pregnancy in the pre-pandemic period, that pregnancy is a valid control, as long as the woman is not matched to herself. Here the assumption is that pregnancies are independent. A sensitivity analysis will be conducted, removing women who are vaccinated in the six weeks preconception – and her controls – from the analysis.

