*Note that only women who have been followed-up to the end of the outcome-specific follow-up period at the end of each study period (i.e. 29 February 2020 for pre-pandemic controls and data of data extraction for pandemic controls) are eligible to be controls for a given outcome analysis.

3.7: Power calculation for matched cohort

It is estimated that by the end of 2021, full outcome and follow-up data will be available for approximately 5,000 vaccinated pregnant women, and by end of 2022, data available for 10,000 vaccinated pregnant women⁶.

Outcomes can be grouped as frequent (risk approximately 10%), moderate (approximately 3%), and rare (approximately 0.5%). Risk estimates for each adverse outcome are provided in Table 2. Based on these estimates and assumptions, with the relative risk of an event occurring post-vaccination set at 0.5, 1.2 and 2.0, and with statistical significance set at 0.05 and 0.01; power calculations for the various scenarios were calculated and are shown in Table 6. The power to detect a relative risk of 0.5, based on 5000 vaccinated pregnant woman against 15000 controls (ratio 1:3), when estimated

⁶ Personal communication with [name], July 2021.

adverse event occurrence is 0.5%, is 94%. This means that the study has a 94% chance of having a p-value of less than 5% (a statistically significant result and strong evidence against the null hypothesis) if there is really a difference in risk between vaccinated and unvaccinated women.

If the statistical power is low, the study sample size may be too small to detect any differences (i.e. under-powered) and therefore null results will need to be interpreted with caution. By convention, 80% is an acceptable level of power. It is acknowledged that the study may be under-powered to identify rarer outcomes.

Table 6: Power calculations scenarios

Cases	Controls	Estimated risk	Relative risk	Power %
5000	15000	0.50%	0.5	94
			1.2	10
			2.0	66
		3.00%	0.5	100
			1.2	45
			2.0	100
		10.00%	0.5	100
			1.2	94
			2.0	100
10000	30000	0.50%	0.5	100
			1.2	17
			2.0	94
		3.00%	0.5	100
			1.2	75
			2.0	100
		10.00%	0.5	100
			1.2	100
			2.0	100

4.0: Data Analyses

4.3: Descriptive analyses

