5.0 Potential limitations

There are a number of limitations that need to be considered when conducting the analysis and interpreting the results. Some of the key limitations are as follows:

1. Lag in data becoming available for women recently captured within the COPS study database:
Due to the way the COPS cohort is derived, there is a lag of up to three months before conceptions are identified and hence the corresponding pregnancies included in the study dataset. This is because either antenatal booking, or an early spontaneous pregnancy loss or termination of pregnancy prior to booking, must occur, and the relevant record be returned to PHS, prior to the pregnancy being identified and the conception retrospectively imputed. These events will usually occur within three months of conception. The COPS cohort is refreshed monthly: more frequent refreshes are not feasible as key source datasets (in particular SMR02) are only updated monthly. This means that, using any month's COPS cohort plus up-to-date vaccination data, will likely fail to identify some recent vaccination events as occurring during early pregnancy. These will be picked up in subsequent months as the COPS cohort is refreshed. This means that initial data outputs must be understood as provisional.
2. Capture of early pregnancy loss:
Women who have early pregnancy loss and do not seek medical advice will not be captured in the COPS dataset.
3. Insufficient sample size for rare outcomes:
For rarer outcomes, there may be insufficient power to assess the association between vaccination status and the outcome using a matched cohort study design. We will still provide descriptive data for these outcomes and, as mentioned in Section 4.5, we will consider different analytical approaches for rare outcomes.
4. Missing data:
For some covariates, there will be missing data, but this is expected to be minimal based on ongoing assessments of data quality.
5. Recording errors:

There may be errors in recording the pregnancy, maternity or neonatal outcomes and the way in which outcomes are recorded may have changed over time.

6. Unmeasured confounding:

There is the potential for unmeasured confounding given the inherent differences between vaccinated and unvaccinated women which might not be accounted for. Specific examples include occupation, specific comorbidities, and wider healthcare seeking behaviours including engagement with antenatal care.

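### Section 3.5.1 keeps recent pregnancies in the analysis if the event has occurred and drops them if it has not, which biases the primary miscarriage comparison towards harm

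*Protocol*

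**What the plan says.** Section 3.5.1 sets the completed-follow-up rule for both the pre-pandemic and the pandemic period: "Women without an observed outcome who had not completed follow-up to the end of the follow-up period for a specific outcome" "will not be eligible for inclusion in the analysis for that outcome". The exclusion is limited to women without the event. The same section says that outcomes are classified as yes or no and that time to event is not modelled, so there is no censoring.

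Section 3.6 words the rule for pre-pandemic controls without an event exemption: "Only women who had been followed-up to the end of the outcome-specific follow-up period on the 29 February 2020 are eligible to be controls". The Table 5 note extends this to all control groups: "only women who have been followed-up to the end of the outcome-specific follow-up period at the end of each study period".

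For vaccinated women, the Table 2 note makes inclusion "dependent on the woman being followed-up to the end of the outcome-specific follow-up period", but only for outcomes whose vaccination timing is given as any. Miscarriage (vaccination timing "Up to 23w+6d gestation") and preterm birth ("Delivery at <37 completed weeks gestation") have fixed gestational limits, so that note does not reach them. For these outcomes 3.5.1 is the only follow-up rule for the vaccinated group.

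Section 3.3 places pre-pandemic controls between 1 January 2015 and 29 February 2020, and vaccinated women between 8 December 2020 and an extraction date that is not fixed. Section 3.7 names end 2021 and end 2022 as the points at which data should be available.

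**The concern.** Eligibility depends on the outcome. Take two women vaccinated at 8 weeks, six weeks before extraction. Neither has reached 24+0. The one who has miscarried enters the analysis and the one who is still pregnant does not, so events are added without the pregnancies that were at risk alongside them.

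This happens near the end of each accrual period. In the vaccinated group that stretch is a large share of all index dates. In the control group it is a small share of more than five years. Primary-analysis matching on maternal age, gestational age and season does not balance distance to the cut-off, and nothing later in the plan corrects for it.

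Miscarriage is a primary outcome of a safety study. The rule distorts the absolute risk in vaccinated women (objective 1) and the comparison (objective 2), and section 6.0 foresees sharing a signal with the regulator. More data of the same kind would narrow the interval around a biased estimate.

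**Working it through.** The protocol gives no figure for this, so there is nothing of its own to reproduce. The check asks what OR the rule produces when vaccination has no effect.

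**Inputs from the protocol.** Miscarriage window to 23+6; background risk 10% to 20% for miscarriage and 7% for preterm birth (Table 2). Control period 1,886 days, or 269 weeks. Vaccinated period 389 days (55.6 weeks) to end 2021, or 754 days (107.7 weeks) to end 2022.

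**Assumptions not in the protocol.** Uniform accrual of index dates; index at 8 weeks; exponential time from index to loss with mean 3 weeks, rescaled to finish within the window; losses recorded at once.

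**Formula.** Let A be the weeks of accrual, R the weeks from index to the end of the window, p the residual risk, F(u) the share of eventual losses that have occurred u weeks after index, and I the integral of F from 0 to R. Completed windows contribute in proportion to A − R, and incomplete windows contribute events only:

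recorded risk = [p(A − R) + pI] / [(A − R) + pI]

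Against controls at risk p, this simplifies to OR = 1 + I/(A − R), which does not depend on p.

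**Index at 8 weeks.** R = 16 and I = [16 − 3(1 − e^(−16/3))] / (1 − e^(−16/3)) = 13.08.
- End 2021: 1 + 13.08/39.6 = 1.33. A 10% risk is recorded as 12.9%.
- End 2022: 1 + 13.08/91.7 = 1.14. A 10% risk is recorded as 11.3%.
- Accrual of only 34 weeks: 1 + 13.08/18 = 1.73. A 10% risk is recorded as 16.1%.

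**Sensitivity.**
- Index at 12 weeks (R = 12, I = 9.22): 1 + 9.22/43.6 = 1.21 and 1 + 9.22/95.7 = 1.10.
- Loss records delayed by 4 weeks, index at 8 (I = 9.10): 1 + 9.10/39.6 = 1.23 and 1 + 9.10/91.7 = 1.10.
- Mean time to loss of 2 or 4 weeks: 1.35 or 1.31 at end 2021.

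**Second model.** Here gestation at vaccination is uniform from six weeks before conception to the end of the window, 85% of miscarriages occur before 14 weeks, preterm risk rises from 32 weeks, and controls are matched on gestation. The first three columns are ORs by days of accrual under a true null, with every control required to complete the window.

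| Outcome | 245 days | 389 days | 754 days | Vaccinated events from incomplete windows |
|---|---|---|---|---|
| Miscarriage, 10% | 1.77 | 1.33 | 1.14 | 46%, 26%, 13% |
| Miscarriage, 20% | 1.68 | 1.31 | 1.13 | 46%, 26%, 12% |
| Preterm birth, 7% | 1.19 | 1.09 | 1.03 | 16%, 8%, 3% |

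**Exemption also given to controls.** Miscarriage at 10%: 1.69, 1.27, 1.08. Preterm birth: 1.18, 1.07, 1.02.

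**Simulation.** A 1:3 conditional logistic analysis (10%, 389 days) gave an OR of 1.38 with pre-pandemic controls. With controls matched on date it gave 0.98 if all controls must complete follow-up and 0.94 if both groups have the exemption, about 1 within simulation error. A date-matched control at the same gestation has the same window end. A recent event therefore finds no eligible control, or sits in a set made up only of events.

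**After the fix.** With eligibility set by the window's calendar end in both groups, the null OR is 1.00.

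**The case against.** Several points on the other side stand.

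- A reader might infer that the main fault is a contradiction between 3.5.1 and section 3.6 with the Table 5 note, so that the two arms are selected by opposing rules. The text does not require this. Section 3.5.1 covers both periods, and a woman who has miscarried has no follow-up left for that outcome, so the control wording can be read as shorthand for the same rule. The wording also matters little: giving controls the exemption moves the OR only from 1.33 to 1.27 at 389 days.
- A reader might infer that all three analyses are affected. Supplementary analyses 1 and 2 match on calendar date, which largely removes the bias from the OR. They offer a planned comparison against a false signal, though they do not repair the primary analysis.
- A reader might pair preterm birth with miscarriage. The figures do not support that.
- A reader might take an OR near 1.7 as the expected size. That needs about 34 weeks of accrual, and the horizons in section 3.7 are longer.
- Section 5.0 notes that a pregnancy becomes visible only once "either antenatal booking, or an early spontaneous pregnancy loss or termination of pregnancy prior to booking, must occur" and the record has been returned, and it calls initial outputs provisional. Delayed loss records shrink the bias without removing it. The provisional label concerns missed recent vaccinations and does not mention this selection.
- For miscarriage, recent pregnancies do not enter strictly as events only, since recent terminations are modelled as a competing outcome (section 4.4).

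None of these points makes inclusion independent of the outcome in the primary analysis.

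**Conclusion.** The rule is wrong as written. In the primary analysis it biases miscarriage towards harm, with a null OR of about 1.3 for extraction at end 2021 and 1.14 at end 2022. These sizes rest on uniform uptake, index at 8 weeks and prompt recording, none of which the protocol gives. Shorter effective accrual raises them; later vaccination or delayed loss records lower them. The direction does not depend on these choices. The effect on preterm birth is small and the difference in wording between sections is secondary.

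The scope should not be read as limited to outcomes with a fixed gestational end. The exemption can affect any outcome whose event may precede the end of follow-up. An ectopic pregnancy ends early, while under 3.5.1 an event-free comparator must reach the end of pregnancy; section 4.4 allows ongoing pregnancies as reference for early outcomes but does not reconcile this with 3.5.1. Maternal outcomes followed to the end of the postpartum period are exposed in the same way, and for them the Table 2 note, which has no exemption, conflicts with 3.5.1. No size was computed for these outcomes.

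**What to change.** Delete the event exemption in 3.5.1 and decide eligibility by calendar date alone, whether or not the event occurred, in every group: vaccinated women, pre-pandemic controls, pandemic controls and the Appendix 3 infection cohorts.

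- Fixed-gestation outcomes: admit a pregnancy only if the date on which it reached, or would have reached, 14+0, 24+0, 32+0 or 37+0, counted from estimated conception, falls before the cut-off. For preterm outcomes, which Table 2 lists under live births, also state how a woman past 37+0 but undelivered is counted.
- Outcomes followed to the end of pregnancy, with or without the postpartum or neonatal period: apply a conception-date cut-off that lets a full-term pregnancy and that added period finish before the cut-off.

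Use one sentence in 3.5.1, 3.6 and the Table 5 note, and bring the Table 2 note into line.

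The cost is a rewording and a date filter on the extract. Some recent events are not counted until the next extraction, so early reports rest on fewer vaccinated pregnancies.

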Pregnant women will be identified through the COPS² study database if they appear on one or more of the data sources listed for the identification of pregnant women in Table 1.

Table 1: Overview of data sources used for analysis

Data	Data source

Datasets required to identify pregnant women in the general population and associated pregnancy start and end dates:
	
 • New national data return developed as part of the response to the COVID-19 pandemic providing information on women booking for antenatal care with NHS maternity services: for identification of women with ongoing pregnancies in near real-time (all other records that identify end of pregnancy events) • GP consultation data: for identification of women with early miscarriage or ectopic pregnancy not managed in hospitals • Scottish Morbidity Record (SMR) 01: for identification of women with early miscarriage or ectopic pregnancy managed in hospitals • Termination of pregnancy statutory notifications (AAS records) • SMR 02: for identification of later miscarriage, stillbirth, and live births managed in hospital (and some home births) • National Records of Scotland (NRS) statutory stillbirth registrations • National Records of Scotland (NRS) statutory live birth registrations • New national data return developed as part of the response to the COVID-19 pandemic providing information on live births notified by maternity services to NHS Board child health administrative departments: for near real-time access to data that allows intergenerational linkage of records relating to mothers and their babies. 
Note that this is already established as part of the COPS study and methodology is set out in the Protocol for estimating the number of COVID-19 vaccinations delivered to pregnant women in Scotland and for describing the uptake and coverage of vaccination in the pregnant population.

Datasets required to identify characteristics of pregnant population
	
 • Covariates of interest include: Maternal age, deprivation score, urban/rurality score, ethnicity, pre-pregnancy clinical vulnerability exc diabetes, diabetes, BMI, smoking status, and linked PCR test data to capture confirmed cases of COVID-19 infection. 
Note that all are available through the COPS study database.

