Appendix Table 3: ICD-10 codes for identifying hypertensive disorders of pregnancy

ICD-10	Condition
O11	Pre-eclampsia superimposed on chronic hypertension
O13	Gestational [pregnancy-induced] hypertension
O14.0	Mild to moderate pre-eclampsia
O14.1	Severe pre-eclampsia
O14.2	HELLP syndrome
O14.9	Pre-eclampsia, unspecified
O15.0	Eclampsia in pregnancy
O15.1	Eclampsia in labour
O15.2	Eclampsia in the puerperium
O15.9	Eclampsia, unspecified as to time period
Considered but not included for this category	
O10	Pre-existing hypertension complicating pregnancy, childbirth and the puerperium
O12	Gestational [pregnancy-induced] oedema and proteinuria without hypertension
O16	Unspecified maternal hypertension

SMR01 and SMR02 records with a relevant date of admission and any relevant ICD10 code recorded against main condition or any other condition will be used to identify admissions for the above 3 conditions. All SMR02 record types will be included (i.e. antenatal, delivery, and postpartum admissions).

Appendix 2: Rationale for selection of pregnancy-related outcome measures to be used in COPS study to assess impact of COVID-19 infection and safety of COVID-19 vaccination

A list of outcomes to be examined post-infection was drawn up in May 2020 for the initial COPS protocol document, based on what was known about COVID-19 at that point. A provisional list of outcomes to be examined post-vaccination (as part of vaccine safety monitoring) was drawn up in April 2021, based on a review of the following sources conducted up to 12 Feb 2021.

- MHRA public assessment record for the Pfizer vaccine (released at the time the MHRA first gave approval for use on 2 Dec 2020) - <https://www.gov.uk/government/publications/regulatory-approval-of-pfizer-biontech-vaccine-for-covid-19>
- MHRA public assessment record for the Oxford vaccine (released at the time the MHRA first gave approval for use on 30 Dec 2020) - <https://www.gov.uk/government/publications/regulatory-approval-of-covid-19-vaccine-astrazeneca>. No public assessment records for other vaccine types available at the time of review
- Data from the MHRA on possible adverse events reported through the Yellow Card scheme up to 31 Jan 2021. <https://www.gov.uk/government/publications/coronavirus-covid-19-vaccine-adverse-reactions>

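### Pandemic-period follow-up is judged complete by the extraction date, not by whether the outcome records have arrived, so late records can lower event counts on the vaccinated side of the primary analysis only

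*Protocol*

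**What the plan says.** Section 3.5.1 classifies each woman as having the outcome or not, and sets the admission rule for incomplete follow-up. It removes "Women without an observed outcome who had not completed follow-up to the end of the follow-up period for a specific outcome"; for the pandemic period this means "outcome-specific follow-up period not completed before date of data extraction". The Table 5 note applies the extraction date to pandemic controls. For the primary comparison, section 3.6 states: "Only women who had been followed-up to the end of the outcome-specific follow-up period on the 29 February 2020 are eligible to be controls".

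The sources differ in speed. Table 1 lists a live-birth notification return "for near real-time access to data that allows intergenerational linkage of records relating to mothers and their babies", and a booking return that identifies ongoing pregnancies in near real time. For outcomes it gives "Sources include: SMR01, SMR02, national linked anomaly database, SICSAG critical care admissions, NRS deaths". Appendix 1 finds hypertensive disorders, venous thromboembolism (VTE) and bleeding from "SMR01 and SMR02 records with a relevant date of admission and any relevant ICD10 code recorded against main condition or any other condition". Section 5.0, limitation 1, says of the cohort that "more frequent refreshes are not feasible as key source datasets (in particular SMR02) are only updated monthly". That limitation concerns late identification of conceptions, and hence of vaccinations in early pregnancy. It does not mention late outcome records in women already included.

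**The concern.** The rule measures elapsed time, not the arrival of records. A recently vaccinated woman can be known to the database from a booking or birth notification, reach the end of her outcome window, and enter the analysis before the record carrying her event has been returned. Where no record is read as no event, she counts as event-free.

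Primary-analysis controls finished follow-up about 22 months before an end-2021 extract, so their records have had ample time to arrive. The loss of events would fall on one side of the comparison. Controls in supplementary analyses 1 and 2 are matched on calendar date and sit under a similar lag. The primary and supplementary results could then differ for an administrative reason, while section 3.6 would lead a reader to look for a pandemic effect.

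**Working it through.** **Inputs from the protocol.** About 5,000 vaccinated women with full data by end 2021 and 10,000 by end 2022 (3.7); 1:3 matching; frequent-outcome risk 10%; relative risk (RR) 1.2 (3.7, Table 6); postpartum window E to E+41 (Table 2 notes); monthly SMR02 updates (5.0). Arrival times for SMR01, SICSAG, deaths and the anomaly database are not given.

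**Assumptions.** Even accrual through 2022; a one-month lag; a share m of the affected women's event records outstanding, varied from 0.25 to 1.

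**1. The plan's own figure.** Table 6 gives 94% power for 5,000 v 15,000 at 10% risk and RR 1.2. A two-proportion test (pooled null variance, two-sided 0.05) gives 0.942 if the vaccinated risk is 0.10/1.2, and 0.975 if it is 0.10 × 1.2. The second is the harm direction and is used below. The difference between them is a separate matter.

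**2. Which events are exposed.** For hypertensive disorders, VTE and bleeding, a woman becomes eligible at least 41 days after delivery. A monthly cycle is at most 31 days, so at least one update falls between delivery and eligibility, with 41 − 31 = 10 days to spare. If the monthly cycle is the only delay, antenatal and delivery diagnoses are in. At worst, puerperal events after about E+10 may be missed.

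Outcomes whose window ends at a gestation or at E have no such allowance. For miscarriage, a woman known from booking can pass 23+6 weeks by the calendar, and section 4.4 allows ongoing pregnancies as the reference for early outcomes. A loss shortly before the window closes could still be unrecorded; a much earlier one has had time to arrive. The problem does not arise where the record that shows the pregnancy has ended also carries the outcome.

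**3. Share of women touched.** (10,000 − 5,000)/12 ≈ 417 a month. One month's lag: 417/5,000 = 8.3% at end 2021; 417/10,000 = 4.2% at end 2022.

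**4. Effect on the estimate.** Observed RR = true RR × (1 − f × m), with f the share touched.

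| One-month lag | m = 0.25 | m = 1 |
|---|---|---|
| End 2021, true RR 1.0 | 0.98 | 0.92 |
| End 2021, true RR 1.2 | 1.18 | 1.10 |
| End 2022, true RR 1.0 | 0.99 | 0.96 |
| End 2022, true RR 1.2 | 1.19 | 1.15 |

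The plan reports odds ratios. At 10% risk, RR 0.917 is an OR of (0.0917/0.9083)/(0.10/0.90) ≈ 0.91. Power to show a true RR of 1.2 at 10% risk, end 2021, falls from 0.975 to between 0.93 (m = 0.25) and 0.52 (m = 1).

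**5. The opposite effect of the same sentence.** Women whose window is still open stay in if they have an event and leave if they do not. Let the open-window group be a fraction g of the cohort and let h be the share of its events already seen. Observed risk = (p + gph)/(1 + gph). At end 2021 and p = 0.10:

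- one month of women, h = 0.5: g = 0.0833, risk 0.1037, RR 1.04
- 1.4 months (about six weeks), h = 1: g = 0.1167, risk 0.1104, RR 1.10

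Both h and the month counts are assumptions. The upward pull is of the same order as the downward one.

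**The case against.** The strongest reply has four parts.

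- **The postpartum window is a buffer.** It is, for the three SMR-coded maternal outcomes. Much postpartum haemorrhage and most hypertensive diagnoses would be expected on antenatal or delivery records. This stands, and it leaves mainly late puerperal events exposed unless returns take longer than the monthly update.
- **The size has no anchor.** This also stands. A reader might suppose that 20% to 30% of all vaccinated women's records are outstanding, which would pull the OR far below 1. At 5,000 women, 20% is 1,000 women, or 1,000/417 ≈ 2.4 months (73 days) with no records at all. Adding the 41 days means delivery records absent for about 3.7 months; for 30% it is about 5 months. Nothing in the protocol suggests this. The three-month lag in limitation 1 is for identifying conceptions.
- **Completeness may be handled elsewhere.** Table 1 refers the cohort methodology to another protocol, and section 3.7 speaks of full outcome data. This stands only in part. Section 3.7 is a forecast of numbers, whereas 3.5.1 and Table 5 state an eligibility rule and fix its date.
- **There are safeguards.** Outputs are called provisional, the cohort is refreshed monthly, and calendar-matched controls share the lag. These help but do not correct the primary estimate. The planned time plots run from vaccination or matching to outcome, not back from extraction, so they would not isolate late records.

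**Conclusion.** The rule is stated and can be followed as written, and doing so can lower event counts in recent vaccinated women without touching the pre-pandemic controls. The point concerns the primary analysis, and chiefly outcomes without a postpartum buffer.

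Under a one-month lag with even accrual, the effect on a true RR of 1.0 is bounded at about 0.92 at end 2021 and 0.96 at end 2022, and it shrinks as the cohort grows. A longer return delay or later-weighted accrual would enlarge it. The documents give no figure for either.

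A reader might infer that harm is masked. The documents do not support this. Section 3.5.1 also keeps recent women with an observed outcome and drops those without, which pushes the estimate up by a similar amount, so the net sign is not fixed. This is a low-cost improvement to the eligibility rule, not a fault that invalidates the analysis.

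**What to change.** In 3.5.1, 3.6 and Table 5, replace the extraction date as the end of pandemic follow-up with an outcome-specific data-completeness date: the latest date to which the slowest source feeding that outcome is judged complete. Admit only women whose window closed by that date. Apply it alike to vaccinated women and pandemic controls, and to women with and without an event; the last condition also removes the upward pull.

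The cost is wording and a deferral of the most recent weeks of pregnancies to a later refresh. Ending eligibility one month earlier at end 2021 takes the vaccinated group from 5,000 to about 4,583. With vaccinated risk taken as background × RR, power changes as follows:

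- 10% risk, RR 1.2: 0.975 to 0.963
- 3% risk, RR 1.2: 0.555 to 0.521
- 0.5% risk, RR 2.0: 0.948 to 0.932

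At end 2022 (10,000 to about 9,583) the 3% figure goes from 0.834 to 0.819, and the other two change by no more than 0.001.
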